4.1 Main Study Objective

The main objective of our study is to determine if treatment with sirolimus can improve clinical outcomes in hospitalized patients with COVID-19.

4.2 Primary Endpoint:

Progression to respiratory failure requiring advanced support measures, either due to inadequate ventilation (non-invasive or invasive mechanical ventilation) or inadequate oxygenation (CPAP* or high flow supplemental oxygen at rates \geq 15 liters/minute), in patients given sirolimus compared to the placebo group.

4.3 Secondary Endpoints:

Key secondary endpoints:

- Escalation in level of care
- Increase in total lymphocyte count
- Normalization of biomarkers (Ferritin, LDH, and d-dimer)
- Survival to hospital discharge
- Drug safety profile (Incidence and type of adverse and serious adverse events)

Other outcomes measures:

- Fever
- Duration of advanced respiratory support
- Duration of hospital stay (in survivors)
- Time from treatment initiation to death (in non-survivors)
- Need for initiation of other off-label rescue therapies such as Anti IL-6 agents, at the discretion of treating clinicians

* CPAP use for known obstructive sleep apnea will not be considered as disease progression.

5. Study Design

We will employ a randomized, double blind, placebo-controlled study design. 30 patients hospitalized with COVID-19 and meeting the inclusion criteria specified below will be randomized to receive sirolimus or placebo in a 2:1 manner. The treatment regimen and duration are provided in Sections 5.5 and 5.6.

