5.5 Study Drug Treatment

Patients who meet eligibility criteria, provide informed consent and are enrolled in the study will be randomized to receive sirolimus or placebo in a double-blind manner and a 2:1 randomization scheme in favor of sirolimus. The sirolimus dose for the study will be 6mg daily on day 1 followed by 2mg daily for a maximum treatment duration of 14 days, or until hospital discharge, whatever happens first. The study drug will be provided by the drug manufacturer, Pfizer, encapsulated and dispensed by the University of Cincinnati's Investigational Drug Services (IDS) Pharmacy, and given to the patients by their bedside nurse. Patients will be reminded about the side effects of sirolimus. Every attempt will be made to give the medication at the same time every day. Chart reviews will be conducted on a daily basis to determine changes in clinical status, concomitant medications and laboratory parameters. Study specific biomarkers will be measured at baseline and then at days 3, 7 and 14. Section 6.2 provides a detailed description of the study specific schedule of events. Patients will be instructed to

contact the study staff should they experience any side effects. Study drug may be held or reduced in the event of unacceptable side effects.

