6.1 Study and Timeline Overview

Patients will be identified by the medical and research staff at the University of Cincinnati Medical Center and the facilities of the affiliated health systems UC Health, LLC and University of Cincinnati Physicians Company, LLC. Recruitment will take place until 30 evaluable patients have been enrolled, or the incidence of new cases does not permit further enrollment. Patients who meet eligibility criteria, provide informed consent and are enrolled in the study will receive instructions regarding study drug dosage, route and administration. The study drug will be given each morning along with other inpatient medications at roughly the same time every day. Patients will be on the study drug for a maximum duration of 14 days, or until hospital discharge, whatever happens first. In case a patient progresses to require advanced respiratory support, the study drug can continue as scheduled at the discretion of the treating clinician(s). If deemed clinically necessary on a case-by-case basis, in these scenarios the patient may need to be withdrawn ± unblinded.

All study procedures will take place after obtaining informed consent. Details of the informed consent process are provided in Section 6.3. Prior to starting study drug, baseline demographic and clinical variables will be collected along with vital signs, amount of supplemental oxygen required, laboratory biomarkers such as absolute lymphocyte count, ferritin, LDH, and d-dimer, renal and liver function tests, concomitant medications, past medical history, and results of the chest imaging. After study initiation, chart reviews will be conducted on a daily basis to assess vital signs, changes to concomitant medications, lab values, and oxygenation indices. Study-specific biomarkers: absolute lymphocyte count, serum ferritin, d-dimer and LDH will be measured at Day 3, 7 and 14 following study initiation, unless already checked clinically in the 24 hours prior to the testing time.

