6.2 Schedule of Events

Event	Screening ¹	D1	D2	D3	D4	D5	D6	D7	D8	D9	D10	D11	D12	D13	D14 ⁶	F/u ⁷
Informed consent	X															
Demographics	X															
Medical history	X															
Determine study eligibility	X															
Con meds	X	X	X	X	X	X	X	X	X	X	X	X	X	X	X	
Review AEs			X				X								X	
Heart rate/pulse ²	X	X	X	X	X	X	X	X	X	X	X	X	X	X	X	
MAP ²	X	X	X	X	X	X	X	X	X	X	X	X	X	X	X	
Highest daily temperature (F)	X	X	X	X	X	X	X	X	X	X	X	X	X	X	X	
Oxygen saturation ²	X	X	X	X	X	X	X	X	X	X	X	X	X	X	X	
FiO ₂ (%) ^{2, 3}	X	X	X	X	X	X	X	X	X	X	X	X	X	X	X	
Pregnancy test ⁴	X															
LDH ⁵	X			X				X							X	
Ferritin ⁵	X			X				X							X	
D-dimer ⁵	X			X				X							X	
Absolute lymphocytes ⁵	X			X				X							X	
CBC (WBCs, Hb, Platelets) ⁵	X			X				X							X	
Serum creatinine ⁵	X			X				X							X	
AST, ALT ⁵	X			X				X							X	
Advanced resp. support (Y/N)	X	X	X	X	X	X	X	X	X	X	X	X	X	X	X	
Vital status	X	X	X	X	X	X	X	X	X	X	X	X	X	X	X	

¹ Screening visit can be the initial visit if a patient meets all inclusion/exclusion criteria

² Mean recorded value for the 24-hour duration of that day

³ FiO₂ (%) will be recorded if directly available from chart review such as in patients on ultra-high flow devices (vapotherm, optiflow etc.) or in patients on advanced respiratory support. For all other patients, FiO₂ (%) will be calculated based on the following conversion:

Supplemental O ₂ (l/min)	0	1	2	3	4	5	6	7	8	9	10	11	12	13	14
FiO ₂ (%)	21	24	27	30	33	36	39	42	45	48	51	54	57	60	63

⁴ Only required for women of childbearing potential, if not already obtained clinically

⁵ No need to recheck if already drawn clinically in the 24 hours prior to the study-specified time. If not checked clinically, these can be measured as research tests. If COVID-19 biorepository sample obtained on the day of these tests, they can be postponed to the next day.

⁶ In case a patient is discharged from the hospital before the 14-day period, their last hospital day will be treated similar to Day 14 with regards to study assessments

⁷ Long term outcomes following the 14-day study period will be assessed by chart reviews

Abbreviations: AE = adverse event, ALT = Alanine aminotransferase, AST = Aspartate aminotransferase, CBC = complete blood count, F = degrees Fahrenheit, FiO₂ = Fraction of inspired oxygen, Hb = Hemoglobin, LDH = Lactate dehydrogenase, MAP = Mean arterial pressure, WBCs = White blood cells

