7.2 Criteria for terminating the study

Up to 30 patients will be enrolled in this study. The maximum duration of patient participation is 14 days. In the event of any death or Grade IV Serious adverse event (SAE) that is unexpected and attributable to the study agent, enrollment will be suspended, pending Data Safety Monitoring Board (DSMB) review.

8. Study variables and measuring methods

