14.3.4 Adverse events associated with laboratory testing

The following table highlights the laboratory values that are being obtained as part of the study along with the reference range for normal values. While any value outside the reference range will be classified as abnormal, the clinical significance of those abnormal values will be determined based on the criteria set forth in the table. All lab values identified as clinically significant will be marked as an AE. The causality and attribution of the lab value to the study drug, as well as action items with regards to follow-up and management of laboratory values that are listed as clinically significant, will be adjudicated on an individual basis by the study PI.

Laboratory parameter	Reference Range	Reported as clinically significant if
Serum Creatinine	0.50 – 0.99 mg/dl	≥1.5 times baseline
AST	10 – 35 U/L	≥ 105 U/L (3 times ULN)
ALT	6 – 29 U/L	≥ 87 U/L (3 times ULN)
Hemoglobin	11.7 – 15.5 gm/dl	Decrease of ≥2gm/dL from baseline
Total white blood cells	3.8 – 10.8 x 10 ³ /µL	≤ 3 or ≥ 11.5 x 10 ³ /µL
Absolute neutrophils	1500 – 7800 cells/µL	< 1,000 or > 9,500 cells/µL
Absolute lymphocytes	850 – 3900 cells/µL	< 500 or > 4500 cells/µL
Absolute monocytes	200 – 950 cells/µL	< 150 or > 1,500 cells/µL
Absolute eosinophils	15 – 500 cells/µL	< 5 or > 1,000 cells/µL
Absolute basophils	0 – 200 cells/µL	> 500 cells/µL
Platelet count	140 – 400 x 10 ³ /µL	< 120 or > 450 x 10 ³ /µL

Abbreviations: AST = Aspartate aminotransferase, ALT = Alanine aminotransferase, MCH = Mean corpuscular hemoglobin, MCHC = Mean corpuscular hemoglobin concentration, MCV = Mean corpuscular volume, RDW = Red blood cell distribution width.

While the guidance above is meant to cover all laboratory values obtained during the study, we realize that it may not be able to cover all the unique circumstances that can arise during the conduct of a clinical trial. As such, in rare situations, the study PI may change the clinical significance of a lab value outside of the above guidance. We do not anticipate this situation to arise commonly, however, and if deviating from the above range while assigning clinical significance, the reason for this diversion will be clearly outlined in the subject's study binder. Adverse events related to study medication will be tabulated by body system and by severity using the NCI CTCAE v 5.0.

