14.4 Collecting, recording and managing adverse events

14.4.1 Identifying adverse events

Any AE that occurs from the moment the subject has signed the consent form will be recorded and is reportable. Collection time for AEs and SAEs will begin after the screening visit when the consent form is signed and will continue until the end of the treatment.

Adverse events may be discovered through any of these methods:

- Electronic medical record review
- Observing the participant
- Questioning the participant, with standardized questions/procedures.
- Receiving an unsolicited complaint from the participant.
- An abnormal value or result from a clinical or laboratory evaluation can also indicate an AE when determined to be clinically significant by the PI. Pre-specified criteria for abnormal lab values are provided in Section 14.3.4.

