14.4.2 Recording AEs

Throughout the study all identified AEs (serious and non-serious) will be recorded on all appropriate source document and AE case report forms (CRFs) regardless of their severity or relation to the study. A complete description of all AEs will include event description, time of onset, investigator assessment of severity, relationship to study agent or procedures, time of resolution/stabilization of the event, expectedness, determination of whether the AE qualifies as a SAE, and action taken. A change in the severity of the AE will also be documented.

Assessment of severity and relationship will be documented on the source documents or on the CRFs.

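### AE incidence is summarised without time at risk although AE collection stops at discharge, so a crude comparison of the arms would partly reflect days observed

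*Combined protocol and SAP*

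**What the plan says.** Protocol 4.3 lists among the key secondary endpoints "Drug safety profile (Incidence and type of adverse and serious adverse events". It gives no denominator or time base for incidence.

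Protocol 14.4.1 starts AE and SAE collection after the consent form is signed and says that it "will continue until the end of the treatment". Protocol 5.5 gives treatment "for a maximum treatment duration of 14 days, or until hospital discharge, whatever happens first", and 6.1 agrees. Protocol 7.2 adds: "The maximum duration of patient participation is 14 days".

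For early discharges, the footnote to the schedule in 6.2 reads "In case a patient is discharged from the hospital before the 14-day period, their last hospital day will be treated similar to Day 14" as regards study assessments; 6.3 and 8.3 say much the same. The AE review row of that schedule has no mark in the follow-up column. For stays beyond day 14, the variables named in 6.3 are respiratory support, hospital and ICU stay, ventilation and vital status, not AEs.

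On summaries, 14.3.4 says that AEs related to study medication "will be tabulated by body system and by severity using the NCI CTCAE v 5.0". Under 14.1 the DSMB reviews patterns and frequencies of all AEs, and an aggregate report covers severity, attribution and relationship. Sections 14.5 and 14.10.1 provide further DSMB tables. None of these uses patient-days. Protocol section 15 and the SAP contain no AE analysis.

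**The concern.** Read together, these sections make each patient's window for new AEs depend on length of stay, and also on death and withdrawal. These are post-randomisation outcomes, and the trial hopes that sirolimus will improve the clinical course. An arm whose patients go home sooner has fewer days on which an AE can be recorded, so a crude count or percentage mixes toxicity with speed of recovery.

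Sections 13.1.2, 13.2 and 14.5 do not close the gap. They prolong follow-up of patients who terminate early or are withdrawn for AEs, or of AEs already identified. None collects new AEs in patients discharged home.

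At stake is how far the AE table can be read as evidence on the drug's safety, both at the DSMB's four enrolment-based reviews (14.1) and when a phase III trial is considered.

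**Working it through.** The documents give no figure for AE incidence, length of stay or AE observation time, so there is no planned value to reproduce.

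**Inputs from the documents.** Progression 50% on placebo and 25% on sirolimus; 30 patients randomised 2:1, so 20 on sirolimus and 10 on placebo (protocol section 15 and SAP); a 14-day cap on treatment.

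**Assumptions not in the documents.** Progressors are observed for all 14 days. Non-progressors are observed for D = 7 days (range 5 to 10). The daily AE rate L is constant and equal in both arms, at 0.05 (range 0.02 to 0.10).

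**Step 1: mean days observed** = p × 14 + (1 − p) × D.

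| D | Placebo (p = 0.50) | Sirolimus (p = 0.25) | Sirolimus/placebo | Reciprocal |
|---|---|---|---|---|
| 5 | 7 + 2.5 = 9.5 | 3.5 + 3.75 = 7.25 | 0.76 | 1.31 |
| 7 | 7 + 3.5 = 10.5 | 3.5 + 5.25 = 8.75 | 0.83 | 1.20 |
| 10 | 7 + 5 = 12.0 | 3.5 + 7.5 = 11.0 | 0.92 | 1.09 |

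With equal daily rates, expected AEs per patient stand in the ratio of days. The reciprocal is the true daily rate ratio at which AE counts per patient would come out equal, that is, a hidden excess of 9% to 31%.

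**Step 2: crude incidence** = p(1 − e^(−14L)) + (1 − p)(1 − e^(−DL)). At D = 7 and L = 0.05, 1 − e^(−0.7) = 0.503 and 1 − e^(−0.35) = 0.295.

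- Placebo: 0.50 × 0.503 + 0.50 × 0.295 = 39.9%.
- Sirolimus: 0.25 × 0.503 + 0.75 × 0.295 = 34.7%.

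An apparent difference of 5.2 points arises with no true difference in daily risk. Over D = 5 to 10 and L = 0.02 to 0.10, it runs from 1.6 to 9.0 points.

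**Step 3: a drug that is truly worse** (D = 7, placebo L = 0.05). At 1.1 times the daily rate, sirolimus shows 37.4% against 39.9% and still looks safer. At 1.5 times it shows 46.9% against 39.9%, and the excess is visible.

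**Step 4: sampling error.** At D = 7 and L = 0.05, SE = √(0.399 × 0.601/10 + 0.347 × 0.653/20) = 18.8 points. The shift is 5.2/18.8, about 0.3 SE. Over the full range of assumptions the SE is 14 to 19 points.

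**Step 5: where the difference in days sits** (D = 7). Days 1–3 contribute 3 days per patient in both arms, and days 4–7 contribute 4. Days 8–14 contribute 0.50 × 7 = 3.5 on placebo and 0.25 × 7 = 1.75 on sirolimus. The totals are again 10.5 and 8.75, and the whole difference lies in the last interval.

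**The case against.** Several points on the other side stand.

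*The size rests on assumed inputs.* Length of stay, daily AE rate and full 14-day observation of progressors are all supplied here. Equal daily risk in progressors and non-progressors is also doubtful, because 14.3.1 records deterioration of a baseline condition as an AE. If every progressor counts as having an AE, incidence at D = 7 and L = 0.05 becomes 0.50 + 0.50 × 0.295 = 64.8% on placebo and 0.25 + 0.75 × 0.295 = 47.1% on sirolimus. Most of that gap would be real efficacy.

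*Shorter treatment is genuinely shorter exposure.* In-hospital, on-treatment incidence is a legitimate descriptive quantity. Risk need not end at discharge, however, given the terminal half-life of about 62 hours quoted in 11.2.

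*A single pooled per-day rate can mislead the other way.* A loading dose is given on day 1. If AEs cluster in the first days, when everyone is still observed, crude proportions are equal, yet the pooled rate makes sirolimus look 10.5/8.75 = 1.20 times worse. This is why rates by interval are needed.

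*The practical consequence is limited.* No between-arm AE test is planned, and the shift is well inside sampling error. Even so, it is a systematic shift that a confidence interval would not reveal.

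A reader might also infer more than the documents support:

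- *Any toxicity could be masked.* It could not; masking stops at the ratio of observation times, about 1.1 to 1.3 here.
- *AEs are recorded only during dosing.* Collection begins at consent, and patients withdrawn for AEs are followed further (13.2).
- *The tabulation in 14.3.4 is the only summary and covers all AEs.* It covers drug-related AEs, and the DSMB receives other summaries.
- *The bias reverses because progressors are withdrawn.* With D = 7, withdrawing them all at day 3 gives (0.25 × 3 + 0.75 × 7)/(0.50 × 3 + 0.50 × 7) = 6/5 = 1.20; at day 5 it gives 6.5/6 = 1.08. That needs every progressor withdrawn, whereas 7.1 has study drug continue despite escalation of care unless the patient is withdrawn, and 12.3.2 does not make escalation an automatic trigger.

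**Conclusion.** The point holds as a modest reporting weakness. AE incidence is a key secondary endpoint, the window for new AEs closes at day 14 or discharge, and no planned summary shows how long each arm was observed. If exit times differ between arms, crude proportions cannot separate toxicity from days observed.

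Under the plan's own progression rates and the stay assumptions above, sirolimus patients have 0.76 to 0.92 times the observation time of placebo patients, enough to hide a daily excess of roughly 9% to 31%. Both the size and the direction depend on discharge, death and withdrawal patterns that the documents do not give. The documents therefore do not support saying that the safety comparison will be biased in favour of sirolimus. They do support saying that the planned tables could not show whether it is.

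**What to change.** In the SAP, and in the DSMB tables, keep the crude number and percentage of patients with AEs and SAEs, and add by arm:

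- patient-days of AE observation;
- events per 100 patient-days overall;
- the same rate by study interval (for example days 1–3, 4–7 and 8–14) among patients still under observation, so that early clustering does not distort one pooled figure.

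Cumulative incidence with discharge as a competing event is not a remedy. If follow-up runs to first AE, discharge, death or day 14, its day-14 value equals the crude proportion, here again 34.7% against 39.9%.

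The cost is SAP wording and a few table columns. The data are already collected: AE records include "event description, time of onset, investigator assessment of severity" (14.4.2), dosing is reviewed daily (11.4), and discharge and death are recorded (8.5). The downside is small: with 30 patients the interval rates will be imprecise and should be labelled descriptive. The additions also say nothing about events after discharge, which the current window does not capture.

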14.4.2 Recording AEs

Throughout the study all identified AEs (serious and non-serious) will be recorded on all appropriate source document and AE case report forms (CRFs) regardless of their severity or relation to the study. A complete description of all AEs will include event description, time of onset, investigator assessment of severity, relationship to study agent or procedures, time of resolution/stabilization of the event, expectedness, determination of whether the AE qualifies as a SAE, and action taken. A change in the severity of the AE will also be documented.

Assessment of severity and relationship will be documented on the source documents or on the CRFs.

14.4.3 Recording SAEs

SAEs will be recorded on the SAE CRF and will include a narrative of the event signed and dated by the PI.

14.5 Managing adverse events

The study investigator must apply his or her clinical judgment as to whether an AE is of sufficient severity to require that the participant immediately be removed from further receiving

the study agent under the protocol. The investigator must institute any necessary medical therapy to protect a participant from any immediate dangers.

An AE will be followed until any of the following takes place: a) it is resolved, b) participant is stable, c) participant is discharged from the hospital and the PI determines that follow-up is no longer needed.

If an abnormal value or result from a clinical or laboratory evaluation is determined to be an AE, then the evaluation that produced the value or result can be repeated until the value or result returns to normal, or the result can be explained, or the usual standard of care does not require further follow-up, and the participant's safety is not at risk.

Non-serious expected AEs will be submitted to the DSMB in a timely fashion. The events will be presented in tabular form and given to the DSMB at every scheduled meeting. Study investigators are also required to fulfill all reporting requirements of their local institutions.

14.6 Grading and Attribution

14.6.1 Grading Criteria

In addition to determining whether an AE fulfills criteria for a SAE or not, the severity of AEs experienced by study participants will be graded according to the criteria set forth in the NCI CTCAE v 5.0. This document provides a common language to describe levels of severity, to analyze and interpret data, and to articulate the clinical significance of all adverse events. All AEs whether or not listed in the NCI CTCAE manual will be graded on a scale from 1 to 5 according to the following standards in the NCI-CTCAE manual (A semi-colon indicates 'or' within the description of the grade):

Grade 1 = Mild; asymptomatic or mild symptoms; clinical or diagnostic observations only; intervention not indicated.

Grade 2 = Moderate; minimal, local or noninvasive intervention indicated; limiting age-appropriate instrumental activities of daily living (preparing meals, shopping for groceries or clothes, using the telephone, managing money, etc).

Grade 3 = Severe or medically significant but not immediately life-threatening; hospitalization or prolongation of hospitalization indicated; disabling; limiting self-care activities of daily living (bathing, dressing and undressing, feeding self, using the toilet, taking medications, and not bedridden).

Grade 4 = Life-threatening consequences; or urgent intervention indicated.

Grade 5 = Death related to AE.

